#### 3.0 Inclusion/Exclusion Criteria

Subjects must meet all inclusion criteria to be eligible to participate in the study. Inclusion criteria are:

1. Subject and guardian has provided informed consent in a manner approved by the IRB and is willing and able to comply with the trial procedures.

- 2. Subject is receiving occupational therapy to treat identified feeding challenges
- 3. Subject has anxiety related to food as reported by caregiver
- 4. Subject is between the ages of 8-12
- 5. Subject has good reading abilities
- 6. Subject weighs 30 pounds or more

Subjects meeting any of the exclusion criteria at baseline will be excluded from study participation.

#### Exclusion Criteria are:

- 1. Any medical condition that, in the opinion of the investigator, would place the subject at increased risk for participation due to the inability to remove the blanket safely. Examples of diagnoses that would exclude a participant include spinal cord injury, cerebral palsy, and muscular dystrophy.
- 2. Concurrent participation on another research study
- 3. Participants outside of the ages 8-12
- 4. Participants refuse to use the weighted blanket
- 5. If the use of a weighted blanket is contraindicated for any reason
- 6. Participants lacking the reading ability to complete a questionnaire

- 7. Participants who weigh under 30 pounds per parent report and cannot use a commercially available weighted blanket as the minimum weight of a weighted blanket is 3 pounds will be excluded but this exclusion is unlikely due to the inclusion age range
- 8. Participant is not currently receiving occupational therapy to address feeding difficulties

### 4.0 Enrollment/Consenting Process

Children receiving occupational therapy services at Capital Area Speech and

Occupational Therapy to address feeding who have anxiety related to food will be offered enrollment via flyers and word of mouth. The first level of recruitment will include potential participants that have a patient relationship with the principal investigator or are receiving occupational therapy services from another occupational therapist at Capital Area Speech and Occupational Therapy. If 12 participants meeting the inclusion criteria cannot be recruited from Capital Area Speech and Occupational Therapy, the second level of recruitment will occur including other clinics in the Austin, Texas area who have given permission for flyers to be left in their waiting rooms. During the second level of recruitment, potential participants will contact the principal investigator for additional information regarding the study. A flyer will be available to potential participants with information about the study and principal investigator's contact information so that caregivers can ask questions. Potential study participants will only be provided additional information upon request regarding the study.

Recruitment will take place for 2 months and is anticipated to start April 2024 following IRB approval with researchers determining eligibility for the study based on inclusion and exclusion criteria. Participants and at least one guardian of each participant will be required to sign a consent form to affirm that they understand the purpose of this study, risks, and

requirements. To respect potential participant privacy, no information will be collected for research purposes prior to consent form completion. Also, no information of participants who withdraw from this study will be used. To consent to this study, potential participants will be provided with a consent form to review via email prior to signing it. Potential participants will be given an opportunity to speak with the investigator prior to signing the consent form.

No randomization will take place. There will be a control period consisting of usual care occupational therapy lasting 1 month prior to the treatment period lasting 1 month.

#### 5.0 Study Procedures

- 1. Recruitment
- 2. Consent
- 3. Enrollment of participants based on inclusion and exclusion criteria.
- 4. Guardians of enrolled participants will complete the baseline outcome measure

  Food Neophobia Scale for Children (FNSC) questionnaire consisting of 10 questions

  (Pliner, 1994). Guardians of participants will also complete an initial food list on the
  initial food log form including all foods that the participant currently tolerates. Included
  on the initial food log form will be a place for the caregiver to record the age and weight
  of the child. The weight of the child will be used to calculate the appropriate weight of
  the weighted blanket. The weighted blanket will not exceed 10% of the child's body
  weight. Weighted blankets are commercially available through the company yescool for
  children in weights of ten pounds, seven pounds, five pounds, and three pounds. Each
  participant will receive a weighted blanket that is approximately 10% of their body

weight but does not exceed 10% of their body weight. For example, if a child weighs 55 pounds, they will receive a five-pound weighted blanket. The initial food log form including the initial food list and weight of the child will be scanned and returned to the caregiver prior to the control period. The FNSC will be collected.

- 5. Participants will receive occupational therapy services treatment as usual without use of a weighted blanket for 1 month. During this period, participants will complete the S-Anxiety scale of the State-Trait Anxiety Inventory for Children (STAIC) three times per week upon sitting at the table prior to a meal (Spielberger, 1973). The S-Anxiety scale questionnaire will take about 8-12 minutes for a child to complete the first time and 5-8 minutes for repeated administrations. All forms and scales necessary for the control period will be provided to the caregivers prior to the control period of the study.
- 6. After the 1-month control period, caregivers will complete the FNSC and complete the second food list adding any new foods to the initial food log (Pliner, 1994). The principal investigator will collect the FNSC and the initial food log form at this time.
- 7. Following the 1-month control period, participants and their guardians will receive a weighted blanket with verbal and written instructions for use and safety. The participants will continue usual care occupational therapy treatment during the treatment period. The caregivers will be provided with copies of the S-Anxiety scale of the STAIC, new food log, and a copy of the initial food log for reference (Spielberger, 1973). Participants will be instructed to use the weighted blanket for at least 5 minutes and no more than 15 minutes while participating in a quiet enjoyable activity prior to a meal with guardian supervision. Guardians will be responsible to keep the weighted blanket when not in use. Due to busy family schedules, it may not be possible to use

the blanket daily, therefore, the family will be asked to offer use of the blanket a minimum of 3 meals a week. On the days that the weighted blanket was used, the participant will complete the S-Anxiety scale of the STAIC at the table where they will consume the meal, following using the blanket and before eating the food (Spielberger, 1973). The guardians will be asked to record any new foods tried during the meal on the new food log along with the date each time the participant uses the weighted blanket.

- Upon completion of the 1-month treatment period, the guardians will complete the FNSC (Pliner, 1994). The principal investigator will collect the FNSC, new food log, and S-Anxiety scale of the STAIC at this time either through HIPAA protected email or in-person (Spielberger, 1973).
- 10. Once the study is completed the guardians will be gifted the weighted blanket to use as they deem appropriate

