#### **Proposed Pilot Study**

This small experimental pilot study addresses the knowledge gap related to the use of weighted blankets for children with anxiety related to food and eating. My plan includes recruiting a minimum of seven children who receive OT treatment at the clinic where I work and clinics in the surrounding area. However, I would like permission to recruit twelve children due to concerns with attrition. The design of the study will include a control period prior to the treatment period. This study will seek to understand if children improve their ability to self regulate and calm with the use of a weighted blanket when trying new foods. It will also attempt to research whether children improve novel food consumption using a weighted blanket.

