#### **6.0 Study Product Description**

A weighted blanket 10% or less of the participant's body weight will be used under parent or therapist supervision as a calming strategy prior to introduction to new food paired with a preferred stationary task such as watching a video or reading a book.

Weighted blankets are commercially available for children in weights of ten pounds, seven pounds, five pounds, and three pounds through the company yescool (yescool, n.d.). The blankets are made from glass beads and breathable polyester microfiber fabric according to the Amazon website. The glass beads are enclosed in five inch by 5 inch square compartments and stitched by high-density 15000 stitches to secure the glass beads within the blanket. Each participant will receive a weighted blanket that is approximately 10% of their body weight but does not exceed 10% of their body weight. For example, if a child weighs 55 pounds, they will receive a five-pound weighted blanket.

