# 11.0 Study Withdrawal/Discontinuation

Possible reasons for withdrawal from this study:

- 1. Time commitment
- 2. Participant no longer wants to use the weighted blanket
- 3. Use of weighted blanket becomes contraindicated
- 4. Discontinuation from occupational therapy services

Handling withdrawals:

Withdrawal from the study will be accepted and an interview regarding reasons for withdrawal will be completed.

Termination of this study will occur if there are no participants willing and able to participate.

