#### 12.0 Biostatics and Subsidies

A statistical analysis using IBM SPSS Statistics (Version 28) predictive analytics software will be completed. The STAIC S-Anxiety scale mean score during the treatment period will be compared to the control period mean score using paired-samples t-tests (Spielberger,

1973). The control period mean score will be compared to the baseline. Similarly, the raw score from the FNSC during the treatment period and the raw control period score will be compared using paired-samples t-tests to understand if the children demonstrated a statistically significant change in food neophobia (Pliner, 1994). The control period raw score will be compared to baseline raw score using paired-samples t-tests. Nonparametric analysis will be used as necessary.

The average number of foods tried during the control period will be compared to baseline and the average number of new foods tried during the control period will be compared to the average number of new foods tried in the treatment period to understand if more foods were tried when using the weighted blanket. A paired-sample t-test will be completed to compare the control period to the treatment period. Nonparametric analysis will be used as necessary.

A weighted blanket will be provided to each of the participants of this study for their use following the study at no cost to the participant. The weighted blankets will be purchased by the principal investigator. This study is not funded by grants or subsidies.

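### The quiet pre-meal activity is prescribed only in the blanket month, so the S-Anxiety comparison cannot separate its effect from the blanket's

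*Combined protocol and SAP*

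**What the plan says.** **Control month.** Section 5.0, step 5, gives usual-care occupational therapy without a blanket. The child completes the STAIC S-Anxiety scale "three times per week upon sitting at the table prior to a meal". Nothing is prescribed for the minutes before the child sits down, and none of the forms described records what the child was doing.

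**Treatment month.** Under step 7, usual occupational therapy continues. The child uses the blanket, supervised by a guardian, for "at least 5 minutes and no more than 15 minutes while participating in a quiet enjoyable activity prior to a meal". The scale is completed at the table after that session and before eating. Section 6.0 (Study Product Description) describes the blanket as "paired with a preferred stationary task such as watching a video or reading a book".

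**Aim and analysis.** The Proposed Pilot Study text in section 2.0 asks whether children "improve their ability to self regulate and calm with the use of a weighted blanket when trying new foods". Section 12.0 states that the "STAIC S-Anxiety scale mean score during the treatment period will be compared to the control period mean score using paired-samples t-tests".

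**Order.** Section 4.0 rules out randomisation and fixes the sequence: "There will be a control period consisting of usual care occupational therapy lasting 1 month prior to the treatment period lasting 1 month".

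**The concern.** Two things are added to the pre-meal procedure in the treatment month: the blanket and a supervised spell of something the child enjoys. Only the blanket appears in the aim. The outcome is state anxiety, measured just after that spell, when a video or book could plausibly have shifted it.

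If the activity calms the child by itself, the paired difference contains that effect and it would be reported as a blanket effect. No condition has the activity without the blanket, and control-month behaviour before meals is not recorded, so no later analysis can recover the split. A larger sample would not help, because the fault lies in what is being compared. The new-food comparison is exposed too, since the same routine precedes the meals at which new foods are logged.

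At stake is whether a pilot meant to inform therapists, and possibly a later study, credits the right component.

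**Working it through.** There is no figure in the plan to reproduce: 7 and 12 children are given without a calculation, and no alpha, SD or effect size is stated. The check has two parts.

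**1. The two procedures side by side**

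| | Control month (step 5) | Treatment month (step 7, section 6.0) |
|---|---|---|
| Occupational therapy | usual care | usual care, continued |
| Weighted blanket | no | yes, 5 to 15 minutes |
| Quiet preferred activity before the meal | not prescribed, not recorded | prescribed, done with the blanket |
| Guardian supervision of that time | not prescribed | prescribed |
| S-Anxiety scale | on sitting at the table | at the table, after the session, before eating |

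Therapy is planned to be the same in both months, so it is not a prescribed difference. The blanket and the supervised activity are, and they always come together.

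**2. Size of the bias**

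Let B be the blanket effect, A the activity effect, and p the share of control-month scale meals that already follow a similar activity. If the effects add and A is the same in both months, the expected paired difference from these sources is

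B + A − pA = B + (1 − p)A.

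The bias in B is (1 − p)A: all of A when p = 0, half of A when p = 0.5.

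To show what this could do to the test, set B = 0 and let d = (1 − p)A divided by the SD of the paired difference. For a two-sided paired t-test with n children, the probability of a significant result is

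P(|T| > t(0.975, n − 1)), with T noncentral t on n − 1 degrees of freedom and noncentrality d√n.

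Inputs from section 2.0: n = 7 (minimum) and n = 12 (number requested). Assumed: alpha 0.05, the values of A and p, and an SD that does not change with p. Critical values are 2.447 (6 df) and 2.201 (11 df). For example, with n = 7 and d = 0.5 the noncentrality is 0.5 × √7 = 1.323, and the probability is 0.201.

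| Activity effect A (SD) | p | Net d | n = 7 | n = 12 |
|---|---|---|---|---|
| 0 | – | 0 | 5% | 5% |
| 0.3 | 0 | 0.30 | 10% | 16% |
| 0.5 | 0 | 0.50 | 20% | 35% |
| 0.8 | 0 | 0.80 | 43% | 71% |
| 0.3 | 0.5 | 0.15 | 6% | 8% |
| 0.5 | 0.5 | 0.25 | 9% | 12% |
| 0.8 | 0.5 | 0.40 | 15% | 24% |

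If the activity is matched in both months (p = 1), the net d is 0 and this source of bias disappears.

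**The case against.** The strongest reply is that the intervention is openly a package. Section 2.0 never says the blanket alone, and section 6.0 describes blanket use as paired with a stationary task. On that reading, the planned test compares the package with usual care and only the wording needs attention. This carries weight, and it is why restating the aim is an acceptable minimum. It does not remove the problem, because the aim in section 2.0 and the interpretation in section 12.0 name only the blanket.

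A second reply is that this is a small, unrandomised pilot in which time, continued therapy, repeated completion of the scale and expectation confound the same contrast. That is true. Matching the activity would not by itself justify a causal claim about the blanket. This confounder differs from the others in that one instruction takes it out of the prescribed procedure.

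The illustration also has limits:
- The 5% reference assumes that the other biases are zero too.
- The n = 12 column needs every child recruited and retained.
- Variation in p between children would alter the SD.
- Section 12.0 allows a nonparametric test instead.
- The sign of A is unknown. Having to stop a preferred video for a meal could raise anxiety and hide a benefit.

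The figures therefore show a possible scale and do not estimate the actual bias.

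**Conclusion.** The concern holds. As planned, the S-Anxiety comparison estimates the blanket together with the quiet activity against usual care, and it cannot support a statement about the blanket alone. This follows from the procedures and needs no assumption about size.

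The size is unknown. The bias is at most the activity's full effect, and less if children already do something similar before control-month meals. Under the stated assumptions, the chance of a significant result with no blanket effect runs from 6% to 43% at n = 7 and from 8% to 71% at n = 12. The plan should be changed on this point. The change affects what may be concluded and does not make the study unworkable.

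**What to change.** **Minimum.** Restate the aim and the planned conclusion as weighted blanket plus pre-meal quiet activity versus usual care. This costs nothing and makes the claim match the comparison.

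**Preferable addition.** Before the three weekly S-Anxiety meals of the control month, have the child follow the protocol's own quiet-activity routine, supervised and without the blanket. The prescribed pre-meal procedure then differs only by the blanket, and the aim can remain a question about the blanket. It needs one added instruction in the control-month materials. Family time is 3 meals × 4 weeks × 5 to 15 minutes = 60 to 180 minutes.

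This addition has drawbacks. The control month is no longer bare usual care, which also changes what section 12.0's control-versus-baseline comparisons of FNSC and foods tried would measure. The burden may raise attrition: step 7 already allows for busy family schedules, and section 11.0 includes "Time commitment" among possible reasons for withdrawal. Section 4.0 says "no information of participants who withdraw from this study will be used", so each loss matters with 7 to 12 children. If that risk is judged too high, the restatement alone is enough. A line on the control-month form recording what the child did before the meal would then leave usual care intact and show how far the two months differ, although it would not remove the difference.

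**In either case.** State that the fixed control-then-treatment order still confounds the comparison with time, continued therapy, repeated completion of the scale and expectation. Neither change fully isolates the blanket.

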#### 6.0 Sources of Research Material

Data for this study will be gathered by caregiver report via the Food Neophobia Scale for Children (FNSC) questionnaire consisting of 10 questions and parent interview to gather information about the age and weight of the child (Pliner, 1994). Participants will complete the State-Trait Anxiety Inventory for Children (STAIC) S-Anxiety scale consisting of 20 questions (Spielberger, 1973). The guardians will also complete a food log. All data collected from the assessments will be used for research purposes. No data from records will be reviewed for this study. In addition, any protocol deviations or unanticipated problems will be monitored.

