#### 8.0 Subject Safety

This study controls for risk as all use of weighted blanket will be under adult supervision and not during sleep. In addition, the participant can refuse the use of the weighted blanket at any

time during the study limiting any psychological risk or adverse events. Any adverse events will be reported immediately.

Prior to the start of the study, researcher will discuss best practices for weighted blanket use and guardians will be provided with a handout detailing the protocol and safety guidelines. The guardian will have the blanket in their possession and will only offer the blanket during times detailed in the protocol. All subjects will be given the opportunity to exit the program and withdraw consent at any time if they determine that they are no longer able to participate. The researcher will be available via HIPAA compliant email throughout the study to answer any questions that may arise and offer support. In person meetings will also be available upon request. All data collected throughout the program will be maintained on password protected emails and computers to reduce the risk for breach of privacy.

[name] will provide supervision as the faculty sponsor through a weekly check-in via email, phone or zoom meeting with the principal investigator. The principal investigator will notify the faculty sponsor immediately via email with any questions or concerns. The principal investigator will include the faculty sponsor on any emails with the participants to ensure appropriate monitoring. All information pertaining to this study will be available to [name].

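### S-Anxiety is scored only on blanket-use days in the treatment month but without that condition in the control month, so the paired comparison is biased if occasional non-use tracks that day's anxiety

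*Combined protocol and SAP*

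**What the plan says.** Section 5.0, step 5 (control month): the child completes S-Anxiety "three times per week upon sitting at the table prior to a meal". Nothing about the child's behaviour decides whether a form is filled in.

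Section 5.0, step 7 (treatment month): "On the days that the weighted blanket was used, the participant will complete the S-Anxiety scale", after using the blanket and before eating. No other occasion is named. The weekly minimum concerns offers, not uses: "the family will be asked to offer use of the blanket a minimum of 3 meals a week". The only reason given for non-daily use is busy family schedules. The new food log is filled in "each time the participant uses the weighted blanket", so it too is silent about other days.

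Section 8.0 says that "the participant can refuse the use of the weighted blanket at any" time. The exclusion criteria in section 3.0 include "Participants refuse to use the weighted blanket". Section 11.0 lists no longer wanting the blanket as a possible reason for withdrawal, and section 4.0 says that withdrawn children's data will not be used. Section 6.0 (Sources of Research Material) adds that "any protocol deviations or unanticipated problems will be monitored", without naming a form or saying that a declined offer is a deviation.

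Section 12.0 compares the treatment-period mean with the control-period mean by paired t-test. It gives no rule for days without blanket use.

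**The concern.** The two means sample meals under different rules, and one rule depends on what the child did that day. The outcome is state anxiety in children enrolled for food-related anxiety, so a link between declining the blanket and that day's anxiety is plausible, though nothing in the documents shows it.

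- If non-use falls on the more anxious days, those scores are missing and the treatment mean drops with no blanket effect.
- If non-use falls on the calmer days, the treatment mean rises and a real benefit can be hidden.
- If non-use is unrelated to anxiety, there is no bias.

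No listed form separates refused from not offered, or holds an anxiety score for a non-use day. Form counts and log dates could show that use days were few, but not why, nor how anxious the child was.

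**Working it through.** **No plan figure to reproduce.** The documents give a minimum of 7 children and a request for 12, but no power, alpha, effect size, SD or refusal rate.

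**Inputs from the documents.** n = 7 and n = 12 (section 2.0); three scorings or offers a week for a month, taken as 12 per period (section 5.0); paired t-test (section 12.0).

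**Assumptions.** No true effect; two-sided 5% test; independent normal readings with within-child SD 1; log-odds of refusal changing by a slope of 0.5 or 1 per SD of that meal's anxiety, with the intercept set to give the stated refusal rate; a random child-by-period effect in each month with SD 0, 0.3 or 0.5; one offer per scoring day. A refused offer loses that day's form only if the blanket was not used at another meal that day.

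**Shift.** With refusal share p and mean anxiety m (in SD) on refused occasions, the mean of the remaining occasions is −p·m/(1 − p). At 25% refusal and slope 1 the logistic model gives m = 0.64, so the shift is −0.25 × 0.64/0.75 = −0.21 SD. At 10% and slope 1, m = 0.82, so −0.10 × 0.82/0.90 = −0.09 SD.

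**False-positive rates** (simulation, 20,000 trials per setting; n=7 / n=12, in %):

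| Refusal | Slope | Shift (SD) | Period SD 0 | Period SD 0.3 | Period SD 0.5 |
|---|---|---|---|---|---|
| 5% | 0.5 | −0.025 | 5.4 / 5.4 | 5.1 / 5.1 | 4.9 / 5.1 |
| 5% | 1 | −0.047 | 5.9 / 6.4 | 5.4 / 5.6 | 5.1 / 5.3 |
| 10% | 0.5 | −0.049 | 5.7 / 6.7 | 5.2 / 5.9 | 5.2 / 5.4 |
| 10% | 1 | −0.091 | 8.0 / 10.9 | 6.3 / 8.1 | 6.0 / 6.3 |
| 25% | 0.5 | −0.120 | 9.5 / 13.9 | 7.5 / 9.4 | 5.8 / 7.5 |
| 25% | 1 | −0.213 | 20.0 / 35.0 | 12.5 / 20.5 | 8.8 / 12.4 |

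Slope 0 gives 4.8-5.2%. Slope −1 gives the same shift with the sign reversed. With slope −1, 25% refusal, a true benefit of 0.5 SD and period SD 0.3, power on used meals is 19%/32%, against 31%/53% if all named meals are scored.

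**Cross-check with another model.** If a share u of offers is used and non-use correlates ρ with anxiety, the shift is −ρ·φ(z_u)/u, where z_u is the standard normal quantile of u. For u = 0.9 and ρ = 0.3: −0.3 × 0.1755/0.9 = −0.06 SD. For u = 0.8 and ρ = 0.5: −0.5 × 0.280/0.8 = −0.18 SD. The order of size is the same.

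**With the fix** (25% refusal, slope 1). With all forms completed the shift is 0 and the error about 5%, assuming a refused offer does not itself change anxiety. If a share c of post-refusal forms is completed, a share 0.25(1 − c) is lost:
- c = 0.75: 0.0625 × 0.64/0.9375 = 0.04 SD; error 5-6%.
- c = 0.5: 0.125 × 0.64/0.875 = 0.09 SD; error 8%/11%, 7%/8% and 6%/6% at period SD 0, 0.3 and 0.5.

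**The case against.** **Refusal may be rare.** Children who refuse at baseline are excluded, persistent unwillingness is a listed reason for withdrawal, and withdrawn data are dropped. The stated reason for non-daily use, schedules, has no stated link to anxiety. This stands: only occasional non-use by willing children is at issue, and at the low refusal rates these provisions make more likely the error is near nominal.

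**The model may overstate the link.** The child declines before the quiet activity, whereas the form is completed later at the table. With an assumed correlation of 0.5 between the two moments, the slope 1 shift halves: 0.5 × 0.21 = 0.11 SD at 25% refusal (error 8%/12%, 7%/9% and 6%/7% at period SD 0, 0.3 and 0.5) and about 0.05 SD at 10%. This also stands.

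**Control meals are family-chosen too.** If anxious children also skip 10% of control forms (slope 1), the −0.21 becomes −0.19 when treatment forms are lost likewise, or −0.12 when refusals already cover those days. At 10% refusal, slope 1, the shift becomes −0.08 or 0. Partial cancellation is therefore possible, but not assured.

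**Use-day scoring matches the question.** Section 2.0 asks about calming with use of the blanket. This is a reason to keep a used-meals comparison, but it does not make that comparison free of selection.

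**Reasons could be asked afterwards.** The investigator is in contact with families and monitors deviations, and the guardian handout, which is not reproduced, may address non-use. So a reader who infers that nothing about non-use can be recovered goes too far: reasons could be sought by recall. The scores not taken could not.

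**Conclusion.** The asymmetry is certain from the text; whether it causes bias is conditional. A reader might infer that the plan favours the blanket, or that an error rate near 35% should be expected. The documents support neither. They do not say that non-use tracks anxiety or in which direction, and the 35% needs 25% refusal, slope 1, n = 12 and no child-level drift between months. At 5-10% refusal the shift is about 0.02-0.09 within-child SD with 5-11% false positives. At 25%, an upper anchor, it is 0.12-0.21 SD with 6-35%, and less if anxiety at the offer only partly predicts the table score. All of this rests on assumed rates, slopes and SDs.

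The change is still worth making before the first control month starts. A stated collection rule, not a missing detail, lets selection into the main anxiety comparison; the data needed to judge it would not exist; and the remedy is cheap. Confidence in the practical importance is medium.

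**What to change.** - In both months, have each family name three scoring meals a week in advance, movable for schedule reasons before any offer is made.
- Collect S-Anxiety at every named meal, whether or not the blanket was used. In the treatment month, tick used, refused or not offered.
- Leave the blanket instructions unchanged. Keep the form on other use days, but leave those extra readings out of the all-named-meals mean.
- Report two comparisons with the control mean: (a) all named meals, described as like-for-like sampling of meals under the blanket programme; and (b) used meals, the section 2.0 question, labelled as open to selection. Do not call (a) the effect of offering, because it includes meals where the blanket was not offered.
- Report counts of refused meals, meals not offered, and missing forms.

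**Cost.** Naming meals ahead, one tick box, and a 5-8 minute form on non-use days. Comparison (a) is diluted. An assumed 0.5 SD effect becomes 0.5 × 0.90 = 0.45 SD at 10% refusal and 0.5 × 0.75 = 0.38 SD at 25%. If 10% of named meals are also not offered, and refusal applies to the rest, these become 0.45 × 0.90 = 0.41 and 0.375 × 0.90 = 0.34 SD. From refusals alone (unrelated to anxiety, period SD 0.3), power for n=7/n=12 is 40%/68% against 46%/75% for used meals at 10% refusal, and 30%/52% against 44%/73% at 25%. This is why both are reported.

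**What remains.** Some bias stays if children who refuse the blanket also decline the form. The change does not address the fixed period order, the loss of withdrawn children's data, or the activity specified only in the treatment month ("while participating in a quiet enjoyable activity prior to a meal").
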